### **5.6.4 Selection of Doses in the Study**

The use of an induction dose higher than the approved dose of 160/80 mg (Week 0/2) is supported by exposure-efficacy modeling analyses from the pivotal registration Study M02-403 (anti-TNF naïve subjects) and Study M04-691 (anti-TNF experienced subjects).

The goal of the TDM regimen is to attain and maintain serum adalimumab levels above reasonably high concentration levels in subjects for mucosal healing. Since exposure and endoscopic relationships are not currently available for adalimumab, clinical remission was used for the selection of concentration thresholds to be used in the TDM regimen. Based on the PK analyses of adalimumab concentrations in the adult Crohn's disease studies, Studies M02-403, M04-691 and M02-433, no concentration level could be identified as a significant and reliable predictor of remission. Therefore, the TDM regimen will be based on two concentration thresholds in conjunction with clinical response criteria as expected to occur in the clinical setting. About 75% of the subjects, who were in remission at Week 56 in Study M02-433, had serum concentration levels above 5 µg/mL. The lower concentration threshold for the TDM regimen was selected as 5 µg/mL; thus, any subject below 5 µg/mL concentration will be escalated to ew dosing regardless of their CDAI or hs-CRP level. The second threshold was selected as 10 µg/mL, which is similar to the median concentrations (9.4 µg/mL at Week 56) observed in subjects who were in remission. The subjects with concentration above 5 and below 10 µg/mL may be dose escalated based on clinical response as outlined in the table below. The subjects with serum concentration above 10 µg/mL will not be dose escalated.

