At Week 12, subjects are re-randomized in a 1:1 ratio to one of the two double-blinded exploratory treatment regimens (adalimumab clinically adjusted [CA] regimen and adalimumab therapeutic drug monitoring [TDM] regimen). The re-randomization at Week 12 is stratified by induction treatment regimen, clinical response (CR-70) status at Week 12, and decrease in SES-CD > 50% from Baseline per the site investigator reading at Week 12. Among subjects achieving decrease in SES-CD > 50% from Baseline at Week 12, the randomization is further stratified by achievement of an SES-CD ≤ 4 and at least a 2 point reduction versus Baseline and no subscore greater than 1 in any individual variable using the Week 12 SES-CD value provided by the site. No study drug is administered or injected at the final visit.

Clinically Adjusted (CA) Regimen:

Subjects randomized to the clinically adjusted regimen will receive 40 mg adalimumab every other week beginning at Week 12. The adalimumab dose will be escalated to every week starting as early as Week 14 if the subject's CDAI is ≥ 220 or hs-CRP ≥ 10 mg/L (using results from the prior or current visit). These subjects will also be allowed to escalate at unscheduled visits that may occur only on Weeks 16, 18, 22, 24, 30, 32, 36, 38, 44, 46, 50, 52 and 54. Once subjects in the CA regimen are escalated, they will remain on 40 mg ew dosing.

Therapeutic Drug Monitoring (TDM) Regimen:

At Weeks 14, 28 and 42, the adalimumab dose for subjects randomized to the TDM will be determined by the dose adjustment criteria table (Table 1). Doses will be determined using blinded serum concentrations at the prior visit (Weeks 12, 26 and 40, respectively) as well as the CDAI or hs-CRP values from the current or prior visit. For subjects who meet criteria for dose escalation at Weeks 14, 28 or 42, subjects will receive 40 mg weekly.

Figure 1. Therapeutic Drug Monitoring (TDM) Regimen Schematic

[figure not shown]

[figure not shown]
Table 1. Adalimumab Dose Adjustment Criteria

Adalimumab Dose Adjustment Criteria ^a			
ADA Serum Concentration ^b (ug/mL)	CDAI ^c	hs-CRP ^d (mg/L)	Dose Change?
Clinically Adjusted Regimen			
any	< 220	< 10	no
any	any	≥ 10	yes; dose escalate to ew
any	≥ 220	any	yes; dose escalate to ew
Therapeutic Drug Monitoring Regimen			
< 5	any	any	yes; dose escalate to ew
5 – 10	< 220	< 10	no
5 – 10	any	≥ 10	yes; dose escalate to ew
5 – 10	≥ 220	any	yes; dose escalate to ew
> 10	any	any	no

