5.0 Analysis Populations

5.1 Definition for Analysis Populations

The following populations will be used for analyses in the study:

Modified Intent-to-Treat (mITT) set includes all ITT subjects who achieve clinical response (CR-70) at Week 12. The mITT set is the primary population for the efficacy analysis for the Maintenance Study.

The safety set consists of all subjects who received at least one injection of study drug during maintenance study. The safety set will be analyzed as treated, according to treatment the subject actually received. The safety set will be used only for safety analysis.

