10.0 Efficacy Analysis

10.1 General Considerations

All statistical tests will be two-sided with the significance level of 0.05. Descriptive statistics will be provided. These include the number of observations, mean, standard deviation, minimum, median, and maximum for continuous variables; and number and percent for discrete variables. The analysis will be performed using SAS[®] Version 9.4 or later (SAS Institute Inc., Cary, NC, USA).

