10.2 Efficacy Analyses

This section provides the details of the efficacy analysis for the Maintenance Study.

For these endpoints which are categorical variables, NRI method of imputation will be used for the missing values. LOCF will be used as a sensitivity analysis wherever applicable.

Both LOCF and OC analyses will be performed for continuous endpoints. The LOCF analysis is considered primary for inferential purposes. In addition, Mixed-Effect Model Repeated Measure (MMRM) will be applied as a sensitivity analysis, wherever appropriate, for the longitudinal continuous endpoints.

For endoscopy related endpoints, there will be no LOCF imputation as there is only one post-baseline endoscopy during Maintenance. OC will be used as a sensitivity analysis.

The difference in proportions of subjects between treatment groups will be analyzed using the two-sided Cochran-Mantel-Haenszel (CMH) test adjusted for induction treatment regimen, and decrease in SES-CD > 50% from Induction Baseline per central reading at Week 12. Additionally, the CMH-based two-sided 95% confidence interval (CI) for the difference in the proportions between the treatment groups will be calculated.

The difference in change from Induction Baseline between treatment groups will be analyzed using an ANCOVA model including factors of treatment, induction treatment regimen, decrease in SES-CD > 50% from Induction Baseline per central reading at Week 12 and Induction Baseline values. Parameter estimates with 95% confidence interval and *P*-value will be provided.

All efficacy endpoints for Maintenance Study are non-ranked.

- Proportion of subjects who achieve endoscopic response (SES-CD > 50% from Induction Baseline [or for a Induction Baseline SES-CD of 4, at least a 2 point

reduction from Induction Baseline]) at Week 56 among subjects with endoscopic response at Week 12

- Proportion of subjects who achieve endoscopic remission ($\text{SES-CD} \leq 4$ and at least a 2 point reduction versus Induction Baseline and no subscore greater than 1 in any individual variable) at Week 56 among subjects with endoscopic remission at Week 12.
- Proportion of subjects who achieve endoscopic remission ($\text{SES-CD} \leq 4$ and at least a 2 point reduction versus Induction Baseline and no subscore greater than 1 in any individual variable) at Week 56 among subjects with endoscopic response at Week 12.

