- Proportion of subjects with an SES-CD decrease of ≥ 3 points compared to Induction Baseline at Week 56.
- Proportion of subjects who achieve symptomatic remission, defined as average daily stool frequency ≤ 2.8 (and not worse than Induction Baseline) and

average daily abdominal pain ≤ 1.0 (and not worse than Induction Baseline), at each scheduled visit in Maintenance Study among subjects with Induction Baseline SF ≥ 4.0 and/or AP ≥ 2.0 .

- Proportion of subjects who achieve symptomatic response, defined as average daily stool frequency at least 30% reduction from Induction Baseline and average daily abdominal pain not worse than Induction Baseline or average daily abdominal pain at least 30% reduction from Induction Baseline and average daily stool frequency not worse than Induction Baseline, at each scheduled visit in Maintenance Study among subjects with Induction Baseline SF ≥ 4.0 and/or AP ≥ 2.0 .
- Time to dose escalation in Maintenance Study.
- Proportion of subjects with Inflammatory Bowel Disease Questionnaire (IBDQ) response (increase ≥ 16 points from Induction Baseline) at each scheduled visit in Maintenance Study.
- Proportion of subjects with IBDQ remission (IBDQ ≥ 170 points) at each scheduled visit in Maintenance Study.
- Proportion of subjects achieving response in IBDQ Bowel Symptom domain (increase of IBDQ bowel symptom domain score ≥ 8) at each scheduled visit in Maintenance Study.
- Proportion of subjects achieving response in IBDQ fatigue item (increase of IBDQ fatigue item score ≥ 1) at each scheduled visit in Maintenance Study.
- Proportion of subjects requiring dose escalation to weekly dosing during Maintenance Study.
- Proportion of subjects who achieve clinical remission (CDAI < 150) at Week 56 among subjects requiring dose escalation to weekly dosing during Maintenance Study.
- Proportion of subjects who achieve endoscopic response (decrease $> 50\%$ SES-CD from Induction Baseline [or for an Induction Baseline SES-CD of 4, at least a 2 point reduction from Induction Baseline]) at Week 56 among subjects requiring dose escalation to weekly dosing during Maintenance Study.
- Proportion of subjects who achieve endoscopic remission (SES-CD ≤ 4 and at least a 2 point reduction versus Induction Baseline and no subscore greater

than 1 in any individual variable) at Week 56 among subjects requiring dose escalation to weekly dosing during Maintenance Study.

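### Three Week 56 endpoints compare CA with TDM only among subjects who escalated, a post-randomization subset defined differently in each arm, so the planned p-values and intervals do not estimate a regimen effect

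*SAP*

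**What the plan says.** The re-randomization is described in Maintenance SAP 4.2: "At Week 12, subjects are re-randomized in a 1:1 ratio to one of the two double-blinded exploratory treatment regimens". The efficacy population is defined in SAP 5.1: "Modified Intent-to-Treat (mITT) set includes all ITT subjects who achieve clinical response (CR-70) at Week 12".

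SAP 10.2 gives one general rule for binary endpoints: "The difference in proportions of subjects between treatment groups will be analyzed using the two-sided Cochran-Mantel-Haenszel (CMH) test", adjusted for induction regimen and "decrease in SES-CD > 50% from Induction Baseline per central reading at Week 12", with a CMH-based 95% CI for the difference. SAP 10.1 sets the level: "All statistical tests will be two-sided with the significance level of 0.05". The endpoint list in SAP 10.2 ends with three Week 56 proportions taken "among subjects requiring dose escalation to weekly dosing during Maintenance Study". Nothing exempts them from the general rule or calls them descriptive. Protocol 5.3.3.3 lists the same three endpoints, and Protocol 8.1.4.3 also prescribes CMH and a CI for maintenance categorical endpoints.

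Who escalates depends on the arm (SAP 4.2 and its Table 1):

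- **CA.** "The adalimumab dose will be escalated to every week starting as early as Week 14 if the subject's CDAI is" at least 220, or if hs-CRP is at least 10 mg/L, whatever the drug concentration. Escalation is also possible at 13 listed unscheduled weeks between Week 16 and Week 54.
- **TDM.** A subject below 5 µg/mL "will be escalated to ew dosing regardless of their CDAI or hs-CRP level" (Protocol 5.6.4). Between 5 and 10 µg/mL, escalation needs the CDAI or hs-CRP trigger. Above 10 µg/mL there is none. Decisions fall only at Weeks 14, 28 and 42.

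**The concern.** A comparison restricted to escalated subjects conditions on something that happens after re-randomization, and the assigned arm decides who qualifies. TDM escalators include subjects who meet neither clinical trigger but have low drug levels, and leave out triggered subjects above 10 µg/mL. CA escalators are all triggered subjects, at any concentration. The two CMH factors capture neither the triggers nor the concentration, so stratification does not restore balance.

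The other restricted efficacy endpoints in SAP 10.2 use Induction Baseline or Week 12 status, fixed before the maintenance regimens begin. Only these three condition on a later event. A reader of the report would see a p-value and an interval labelled as a treatment difference, in the same format as the valid mITT comparisons.

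**Working it through.** **No stated figure to reproduce.** SAP 4.3 gives no sample size for the Maintenance Study, and the documents give no escalation rates, so every number below rests on stated assumptions.

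**Step 1: what each rule selects.** One assumption set:

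- mITT of 300, so 150 per arm
- clinical trigger met by 40%
- concentration split (<5 / 5-10 / >10 µg/mL) of 40/30/30% if triggered and 25/28/47% if not

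The second split is guided by Protocol 5.6.4, where about 75% of remitters in an earlier study were above 5 µg/mL and their median was 9.4 µg/mL.

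- CA escalates 0.40 × 150 = 60.
- TDM escalates 0.40 × (0.40 + 0.30) = 0.28 (triggered, up to 10 µg/mL) plus 0.60 × 0.25 = 0.15 (not triggered, below 5 µg/mL). The total is 0.43 × 150 = 64.5.

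The 0.28 is common to both arms. CA adds 0.40 × 0.30 = 0.12 who are triggered and above 10 µg/mL; TDM adds the 0.15 instead. Let *a* be Week 56 remission in the common group, *h* in CA's extra group and *w* in TDM's extra group, with no effect of regimen or dose:

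- CA rate = (0.28*a* + 0.12*h*) / 0.40
- TDM rate = (0.28*a* + 0.15*w*) / 0.43

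**Step 2: the sign depends on *w* and *h*.** Using only the assumed rates 25% and 65%, with *a* = 0.25:

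| Assumption | CA | TDM | TDM − CA |
|---|---|---|---|
| Activity alone matters: *h* = 0.25, *w* = 0.65 | 25.0% | 39.0% | +14 points |
| Both extra groups do well: *h* = *w* = 0.65 | 37.0% | 39.0% | +2 points |
| The extra groups follow concentration: *h* = 0.65, *w* = 0.25 | 37.0% | 25.0% | −12 points |

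**Step 3: rejection rate in the first row.** The pooled proportion is (60 × 0.25 + 64.5 × 0.3895) / 124.5 = 0.322. The null SE is √(0.322 × 0.678 × (1/60 + 1/64.5)) = 0.0838, and the unpooled SE is √(0.25 × 0.75/60 + 0.3895 × 0.6105/64.5) = 0.0825. The rejection rate is about Φ((0.1395 − 1.96 × 0.0838) / 0.0825) = Φ(−0.30) = 38%. Simulating the SAP's four-stratum CMH test gives 35.9%.

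**Step 4: wider simulations with no regimen effect and outcome depending on activity only.**

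- Latent-variable model: 160 per arm, 30% active, 15% to 35% below 5 µg/mL, 30% above 10 µg/mL, activity-concentration correlation −0.2, log odds of remission falling 0.5 to 1.0 per SD of activity. Differences are +5 to +16 points. CMH rejection is 7% to 41%; repeat runs reach 44%.
- Two-state model as in Step 1, over mITT 200 to 400, trigger 30% to 50%, and remission 25% or 35% if triggered against 65% if not. Rejection is 11% to 57%.
- Controls in the two-state model. When the trigger is not prognostic, rejection is 4.4% to 6.0%. The same test in the full mITT set rejects in 4.4% to 5.8%. The inflation therefore comes from the selection.

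**Step 5: letting concentration matter.** In the latent-variable model, with an assumed log-odds slope per SD of concentration (unstratified two-proportion test):

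- concentration 0.5, activity 0.5: −3 to +2 points, rejection 4% to 5%
- concentration 1.0, activity 0.5: −5 to −9 points (favouring CA), rejection 9% to 17%
- concentration 1.0, activity 1.0: −5 to +2 points

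In the two-state case of Step 1, a log-odds penalty of 0.5, 1.0 or 1.5 for levels below 5 µg/mL lowers the difference to +10, +6 or +2 points and rejection to 23%, 11% or 5.5%.

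None of these models represents repeated triggers or the different decision times.

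**The case against.** The strongest reply is that little hangs on these endpoints. The Protocol synopsis calls the maintenance analyses exploratory, SAP 10.2 ranks none of them, SAP 10.3 makes no multiplicity adjustment, and no success criterion uses them. Protocol 1.1 gives their purpose as assessing the effect of escalation, not comparing regimens; they reach a between-arm test only through the general rule. The unrestricted mITT versions are already listed in SAP 10.2. All of this stands, and it limits the importance of the point. It does not answer it: exploratory status weakens the claim a p-value supports but does not make a comparison of differently selected groups unbiased. Nor can comparing escalators across arms show the effect of escalating, since both groups escalated.

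A reader might infer more: that the escalation rules themselves make the comparison favour TDM. The documents do not support that. TDM's rule adds clinically quiet subjects, but it also concentrates low drug levels and drops triggered subjects with high levels. Protocol 3.0 reports better Week 4 efficacy at higher trough concentrations, while Protocol 5.6.4 says no concentration level reliably predicted remission. Together these leave the sign open. Nor is every CA escalator clinically unwell: hs-CRP alone is enough, so a subject with CDAI below 150 can escalate.

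**Conclusion.** The point holds as one of non-comparability. The SAP plans a 0.05-level test and a 95% CI for the CA-TDM difference in a post-randomization subset whose membership rule differs by arm. Neither result estimates a regimen effect, and either can mislead when the regimens are equivalent. That conclusion needs only the SAP's own rules.

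The direction and size are unknown. The figures of about +5 to +16 points for TDM and 7% to 44% null rejection assume that outcome depends on activity and not on concentration; the coarser two-state model reaches 57% on the same premise. With a concentration effect, rejection can fall to about 5% or the difference can turn in favour of CA. These ranges show what could happen and are not estimates for this trial. The full-mITT comparisons and the Induction results are unaffected. The wording should be corrected, but nothing confirmatory depends on it.

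**What to change.** In Maintenance SAP 10.2, state that the three Week 56 endpoints restricted to escalated subjects will be summarized by arm (n, %, within-arm CI), labelled non-randomized, with no between-arm CMH p-value or CI. State that CA-versus-TDM inference on clinical remission, endoscopic response and endoscopic remission comes from the unrestricted Week 56 versions in the full mITT set. Because Protocol 8.1.4.3 prescribes CMH and a CI for maintenance categorical endpoints, record the departure in SAP 12.1.

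The cost is three exploratory p-values with their intervals and one entry in the change summary. No data collection, endpoint definition or dosing rule changes.

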10.3 Handling of Multiplicity

No adjustment for multiplicity will be done.

11.0 Safety Analysis

11.1 General Considerations

All safety analyses will be performed on the safety analysis set. The safety variable will be summarized by treatment according to the treatment a subject actually received.

11.2 Analysis of Adverse Events

11.2.1 Treatment-Emergent Adverse Events

Treatment-emergent AEs during Maintenance Study are defined as events that begin or worsen either on or after the first dose of the study drug and within 70 days after the last dose of the study drug.

The 70-day follow-up phone call will not be required for any subject that initiates commercial adalimumab.

An overview of treatment-emergent AEs, including AEs of special interest such as adverse events leading to death and adverse events leading to premature discontinuation, AEs by Medical Dictionary for Drug Regulatory Activities (MedDRA version 21.0 or later) preferred term and system organ class, AEs by maximum relationship to study drug, and AEs by maximum severity will be summarized by number and percent.

The number and percent of subjects experiencing treatment-emergent adverse events will be summarized for the following adverse event categories.

- Any treatment-emergent adverse event.
- Any treatment-emergent adverse event that was rated as possibly related to study drug by the investigator (Reasonable Possibility).
- Any treatment-emergent severe adverse event.
- Any treatment-emergent serious adverse event.
- Any treatment-emergent adverse event leading to discontinuation of study drug.
- Any treatment-emergent adverse event leading to death.
- Any treatment-emergent adverse event of special interest.
- Any Deaths

Treatment-emergent adverse events will be summarized as follows:

- Grouped by System Organ Class and Preferred Term.
- A by-subject listing will be provided.
- Grouped by System Organ Class, Preferred Term and Severity.
- Grouped by System Organ Class, Preferred Term and Relationship to Study Drug.
- Grouped by System Organ Class and Preferred Term with subject numbers.

In treatment-emergent AE tables, a subject who reports more than one treatment-emergent AE in different system organ classes will be counted only once in the overall total. A subject who reports two or more different preferred terms which are in the same SOC will be counted only once in the SOC total. A subject who reports more than one treatment AE with the same preferred term will be counted only once for that preferred term using the most extreme incident (i.e., most "severe" for the severity tables and most "related" for the relationship tables).

Adverse events will also be summarized by maximum severity. If a subject has an adverse event with unknown severity, then the subject will be counted in the severity category of "unknown," even if the subject has another occurrence of the same adverse event with a severity present. The only exception is if the subject has another occurrence of the same adverse event with the most extreme severity – "Severe." In this case, the subject will be counted under the "Severe" category.

Adverse events will also be summarized by maximum relationship to study, as assessed by the investigator. If a subject has an adverse event with unknown relationship, then the subject will be counted in the relationship category of "unknown," even if the subject has another occurrence of the same adverse event with a relationship present. The only exception is if the subject has another occurrence of the same adverse event with a relationship assessment of "Reasonable Possibility." In this case, the subject will be counted under the "Reasonable Possibility" category, respectively.

Incidence rates per 100 patient years of exposure to study drug will be presented for AE overviews and for AEs by SOC and preferred term where the number of events will be used as the numerator.

All Adverse Events identified to AbbVie from the 70-day follow-up phone call will be collected as source data to be evaluated and reported. Thus, all SAEs and nonserious AEs as defined by AbbVie, reported during the 70-day follow-up phone call must be captured in the clinical database. The end of trial is the last subject contact, i.e., the 70-day follow-up call.

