9.0 Study Drug Exposure and Compliance

Study drug exposure and compliance will be summarized using the mean, standard deviation, minimum, median, and maximum. Exposure to study drug (total patient years) will be summarized by treatment group.

The number of injections received at each schedule time point will be summarized with number and percent for each treatment group.

Study Drug Exposure (in Days) during the Maintenance Study:

- Date of last dose of Maintenance Study drug – Date of first dose of Maintenance Study drug + 14 days

Study Drug Compliance:

Treatment compliance will be summarized for each treatment group in the mITT population. The treatment compliance is defined as the number of injections actually taken by the subject divided by the number of injections planned to be taken by the subject during the Maintenance Study.

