9.0 Study Drug Exposure and Compliance

Study drug exposure and compliance will be summarized using the mean, standard deviation, minimum, median, and maximum. Exposure to study drug (total patient years) will be summarized by treatment group.

The number of injections received at each schedule time point will be summarized with number and percent for each treatment group.

Study Drug Exposure (in Days) during the induction period:

For subjects who discontinued from the Induction Study:

- Date of last dose of Induction Study drug – Date of first dose of Induction Study drug + 14 days

For subjects who completed the Induction Study:

- Date of first dose of Maintenance Study drug or date of first dose study drug in Study M14-347 – Date of first dose of Induction Study drug + 1 day,
Or
- Date of last dose of Induction Study drug + 14 – Date of first dose of Induction Study drug + 1 day, whichever is shorter.

The date of last dose of Induction Study drug is defined as the date of last study drug injection before the date of re-randomization into Maintenance Study. The date of first dose of Maintenance Study drug is defined as the date of first study drug injection on or after the date of re-randomization into Maintenance Study.

Study Drug Compliance:

Treatment compliance will be summarized for each treatment group in the ITT population. The treatment compliance is defined as the number of injections actually

taken by the subject divided by the number of injections planned to be taken by the subject during the induction period.

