11.2 Analysis of Adverse Events

11.2.1 Treatment-Emergent Adverse Events

Treatment-emergent AEs during Induction Study are defined as events that begin or worsen either on or after the first dose of the study drug and within 70 days after the last dose of the study drug for subjects who do not participate in the OLE (Study M14-347) or Maintenance study, or until first dose of maintenance study drug, or until first dose of study drug in the OLE study if the subject who enrolled under Amendment #3 or earlier, is a study completer and is enrolled in the OLE.

The 70-day follow-up phone call will not be required for any subject that initiates commercial adalimumab.

An overview of treatment-emergent AEs, including AEs of special interest such as adverse events leading to death and adverse events leading to premature discontinuation, AEs by Medical Dictionary for Drug Regulatory Activities (MedDRA version 21.0 or later) preferred term and system organ class, AEs by maximum relationship to study drug, and AEs by maximum severity will be summarized by number and percent.

The number and percent of subjects experiencing treatment-emergent adverse events will be summarized for the following adverse event categories.

- Any treatment-emergent adverse event.
- Any treatment-emergent adverse event that was rated as possibly related to study drug by the investigator (Reasonable Possibility).
- Any treatment-emergent severe adverse event.
- Any treatment-emergent serious adverse event.
- Any treatment-emergent adverse event leading to discontinuation of study drug.
- Any treatment-emergent adverse event leading to death.
- Any treatment-emergent adverse event of special interest.
- Any Deaths

Treatment-emergent adverse events will be summarized as follows:

- Grouped by System Organ Class and Preferred Term.
- A by-subject listing will be provided.
- Grouped by System Organ Class, Preferred Term and Severity.
- Grouped by System Organ Class, Preferred Term and Relationship to Study Drug.
- Grouped by System Organ Class and Preferred Term with subject numbers.

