In treatment-emergent AE tables, a subject who reports more than one treatment-emergent AE in different system organ classes will be counted only once in the overall total. A subject who reports two or more different preferred terms which are in the same SOC will be counted only once in the SOC total. A subject who reports more than one treatment AE with the same preferred term will be counted only once for that preferred term using the most extreme incident (i.e., most "severe" for the severity tables and most "related" for the relationship tables).

Adverse events will also be summarized by maximum severity. If a subject has an adverse event with unknown severity, then the subject will be counted in the severity category of "unknown," even if the subject has another occurrence of the same adverse event with a severity present. The only exception is if the subject has another occurrence of the same adverse event with the most extreme severity – "Severe." In this case, the subject will be counted under the "Severe" category.

Adverse events will also be summarized by maximum relationship to study, as assessed by the investigator. If a subject has an adverse event with unknown relationship, then the subject will be counted in the relationship category of "unknown," even if the subject has another occurrence of the same adverse event with a relationship present. The only exception is if the subject has another occurrence of the same adverse event with a relationship assessment of "Reasonable Possibility." In this case, the subject will be counted under the "Reasonable Possibility" category, respectively.

Incidence rates per 100 patient years of exposure to study drug will be presented for AE overviews and for AEs by SOC and preferred term where the number of events will be used as the numerator.

All Adverse Events identified to AbbVie from the 70-day follow-up phone call will be collected as source data to be evaluated and reported. Thus, all SAEs and nonserious AEs as defined by AbbVie, reported during the 70-day follow-up phone call must be captured in the clinical database. The end of trial is the last subject contact, i.e., the 70-day follow-up call.

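### AE rates per 100 patient-years can count events to 70 days after the last dose over exposure that ends at 14 days, for subjects followed off drug

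*SAP*

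**What the plan says.** **Rates.** Section 11.2.1 of each SAP states: "Incidence rates per 100 patient years of exposure to study drug will be presented for AE overviews", and for system organ class and preferred term, "where the number of events will be used as the numerator". The sentence does not cite an exposure definition.

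**Event window, Maintenance.** Section 11.2.1 of the Maintenance SAP takes treatment-emergent events as those that begin or worsen "on or after the first dose of the study drug and within 70 days after the last dose of the study drug". The same section requires AEs reported at the 70-day call to be captured, with one exemption: "The 70-day follow-up phone call will not be required for any subject that initiates commercial adalimumab". Protocol 6.1.4 likewise exempts subjects who stay on adalimumab and sends their new events through post-marketing reporting.

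**Exposure, Maintenance.** Section 9.0 has one formula: "Date of last dose of Maintenance Study drug – Date of first dose of Maintenance Study drug + 14 days".

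**Induction.** For subjects who stop, Section 9.0 of the Induction SAP uses "Date of last dose of Induction Study drug – Date of first dose of Induction Study drug + 14 days", while 11.2.1 counts events "within 70 days after the last dose of the study drug for subjects who do not participate in the OLE" or Maintenance. For completers, events are cut at the first Maintenance or extension dose. Their exposure is the lesser of the interval to that dose and the interval to last dose + 14, each measured from the "Date of first dose of Induction Study drug + 1 day, whichever is shorter".

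Neither SAP defines a separate time at risk, limits rate events to the exposure interval, or adds follow-up time to exposure.

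**The concern.** An incidence rate needs its events and its person-time to cover the same window. Read together, Sections 9.0 and 11.2.1 let a subject followed off drug contribute events for 70 days after the last dose but person-time for only 14. The published figure would then be neither an on-drug rate nor a 70-day on-study rate, although it is labelled as a rate per unit of drug exposure. It is planned for the AE overview and for every system organ class and preferred term, so the mismatch would recur throughout those tables. Readers may compare such rates with those of other adalimumab studies, and there the absolute level matters.

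The Induction SAP brings the two windows close together for completers, which suggests that the mismatch elsewhere is an oversight.

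**Working it through.** The documents state no AE rate, so there is no planned figure to reproduce.

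**Inputs from the documents.** Event window: last dose + 70 days. Exposure: last dose + 14 days. First Maintenance dose: Week 12. Last planned Maintenance injection: Week 55 (Protocol Appendix G).

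**Assumptions, not in the documents.** r is the recorded AE rate off drug divided by that on drug. D is the share who discontinue, on average at mid-period. f is the share of completers followed off drug. All stoppers are taken as followed to day 70.

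**1. Gap.** 70 − 14 = 56 days. One day at most depends on inclusive counting.

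**2. One Maintenance completer followed to day 70.** Week 12 to Week 55 is 43 × 7 = 301 days. Exposure is 301 + 14 = 315; the event window is 301 + 70 = 371.

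- *Against a rate with matched 70-day person-time:* the same events are divided by 315 instead of 371, so the ratio is 371/315 = 1.18 whatever r is. Per 100 such subjects, 100 × 56/365.25 = 15.3 patient-years are left out.
- *Against the on-drug rate:* 1 + r × 56/315, which is 1.18 at r = 1, 1.09 at r = 0.5, 1.04 at r = 0.25 and 1.00 at r = 0.

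**3. Pooled Maintenance, on-drug benchmark.** A stopper has 301/2 = 150.5 days to last dose and 164.5 exposure days. Inflation = 1 + r × 56 × [D + (1 − D)f] / [(1 − D) × 315 + D × 164.5].

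| | D = 0.1 | D = 0.2 | D = 0.3 |
|---|---|---|---|
| r = 1, f = 0 | 1.019 | 1.039 | 1.062 |
| r = 1, f = 0.5 | 1.103 | 1.118 | 1.135 |
| r = 1, f = 1 | 1.187 | 1.197 | 1.208 |
| r = 0.5, f = 0 | 1.009 | 1.020 | 1.031 |
| r = 0.5, f = 0.5 | 1.051 | 1.059 | 1.067 |
| r = 0.5, f = 1 | 1.093 | 1.098 | 1.104 |

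**4. Between Maintenance arms, D = 0.3 against 0.1.** The ratio of the two inflation factors at f = 0, 0.5 and 1 is 1.043, 1.029 and 1.018 at r = 1, and 1.022, 1.015 and 1.010 at r = 0.5. With equal D, r and f it is 1.

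**5. Induction completer on schedule.** Last Induction dose on offset day 70, first Maintenance dose on day 84. Exposure is min(84 + 1, 70 + 14 + 1) = 85 days. Events with onset on the first Maintenance day belong to Maintenance (Induction SAP 6.0), so there are 84 event days. The windows are approximately matched. Small gaps arise off schedule: 87 against 85 days if the Maintenance dose is 3 days late, and 84 against 71 if the Week 10 dose is missed.

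**6. Pooled Induction, on-drug benchmark.** Completers count 85 days, taken as matched; stoppers have 35 + 14 = 49 exposure days and 56 unmatched days. Inflation = 1 + r × D × 56 / [(1 − D) × 85 + D × 49].

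| | D = 0.05 | D = 0.1 | D = 0.2 |
|---|---|---|---|
| r = 1 | 1.034 | 1.069 | 1.144 |
| r = 0.5 | 1.017 | 1.034 | 1.072 |

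**The case against.** **The numerator and denominator are both inferred.** The rate sentence speaks of AEs, not treatment-emergent AEs, and does not point to Section 9.0. This stands and limits confidence. But the sentence sits in the treatment-emergent section, Section 9.0 describes total patient-years in nearly the same terms, and no alternative is given. If another denominator was meant, it still has to be named.

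**A reader might infer that the rates are overstated whatever happens off drug.** That is true only against matched 70-day person-time. Against the on-drug rate it requires AEs recorded between day 14 and day 70. Ascertainment there is thin: Protocol 5.4.1 places the discontinuation visit within 2 weeks of the last dose, after which one call is planned, and subjects who continue adalimumab are exempt. So r = 1 with everyone followed is an upper scenario.

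**A reader might infer that all of Induction is affected alike.** It is not. The Protocol synopsis sends all completers into Maintenance, and their windows nearly coincide. Nor can one say which period is inflated more: at equal D and r = 1, Maintenance exceeds Induction only if f is above 0.14 (D = 0.05), 0.30 (D = 0.1) or 0.67 (D = 0.2), and f is not given.

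**A reader might infer that the safety comparison between arms is biased.** The scenarios do not show material bias. No test is planned on the rates, the number-and-percent tables do not use person-time, and Protocol 8.1.5 asks only for number and percentage. Maintenance outcome analyses are exploratory. These points stand and hold the severity down.

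**Conclusion.** As written, the SAPs pair a 70-day event window with 14-day exposure for Maintenance subjects followed off drug and for Induction subjects who stop and do not continue. This is more than missing detail, because following the stated rules produces rates whose two parts cover different periods.

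The size depends on the benchmark. A Maintenance completer followed to day 70 is overstated 1.18-fold against matched person-time at any off-drug rate, and by 1.00 to 1.18 against the on-drug rate for r from 0 to 1. Pooled on the on-drug benchmark, with r from 0.5 to 1, the inflation is about 1.01–1.21 in Maintenance (10–30% discontinuing, none to all completers followed) and 1.02–1.14 in Induction (5–20% discontinuing). Between-arm distortion is about 1.01–1.04 at 10% against 30% discontinuation. The discontinuation rates, follow-up shares and r are all assumptions.

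Only the absolute level of a descriptive safety output is at stake. Severity is low to moderate, and confidence is moderate because both parts of the rate are inferred.

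**What to change.** In Section 11.2.1 of both SAPs, state that the denominator is Section 9.0 exposure. Count in the rates only events with onset inside that same interval: to last dose + 14 days, or to the end of the capped interval for Induction completers. This fits the existing label, which is per unit of drug exposure. Keep later events in the number-and-percent tables and listings. The cost is SAP wording and programming, using dose and AE onset dates already collected. The downside is that late events leave the rates.

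If a 70-day on-study rate is wanted instead, define time at risk from the first dose of the period to the earliest of last dose + 70 days, last contact, or the next adalimumab dose. Truncate events at the same point and label the rate accordingly. This needs the date of last contact and, where known, the start of continuing adalimumab.

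The two are not interchangeable. For a Maintenance completer followed to day 70, the on-study rate is (315 + 56r)/371 of the on-drug rate: 343/371 = 0.92 at r = 0.5 and 315/371 = 0.85 at r = 0. The SAPs should say which quantity is reported.
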